PROTOCOL

Background

1. Provide the scientific background, rationale and relevance of this project.

Answer/Response:

Transversus Abdominis Plane (TAP) block is a useful tool in pain management after abdominal surgery. It is a regional nerve block that targets T6-L1 thoracolumbar nerves running in the plane between internal oblique and transversus abdominis muscle. It is shown to help with post-operative pain management, reducing pain scores and narcotic pain medication use, as well as promoting earlier return to activity and recovery.^{1,2} TAP block became a very popular, safe, and effective therapeutic adjunct for many different abdominal surgeries ranging from obstetric procedures to general surgery procedures like colorectal surgery.^{3,4} Furthermore, it is used in plastic surgery procedures such as Deep Inferior Epigastric Perforator (DIEP) free flap or Transverse Rectus Abdominis Myocutaneous (TRAM) flap, as they involve extensive amount of abdominal soft tissue incision. Previous studies have shown that TAP block in these procedures significantly reduce post-op pain and narcotic pain medication use.^{5,6} More recently, Exparel (liposomal bupivacaine) has risen to spotlight for providing a longer, sustained local anesthesia. Various surgical disciplines have adopted this agent as part of their pain management protocol. However, there are no literatures that describe the effect of TAP block using Exparel for breast free flap population. We hypothesize that delivering TAP block with Exparel (vs. plain bupivacaine) will provide longer regional blocking effect, hence aiding in pain control and recovery postoperatively.

Objectives/Hypothesis

Answer/Response:

- We hypothesize that liposomal bupivacaine (Exparel) TAP block will provide longer pain control compared to plain bupivacaine TAP block in abdomen-based free flap breast.
- Primary outcome = post-op pain scores during hospitalization, post-op narcotic pain medication use during hospitalization, post-op narcotic pain medication use after discharge (within 30 days of discharge)
- Secondary outcome = Length of stay, Post-op nausea and vomiting (PONV)

Study Design: Biomedical

1. Will controls be used?

Answer/Response: Yes

► IF YES, explain the kind of controls to be used.

Answer/Response: Usual care, TAP block with plain bupivacaine

2. What is the study design?

Answer/Response: Randomized, single-blind control study

3. Does the study involve a placebo?

Answer/Response: No

Human Participants

Ages: 18 and older

Sex: Female

Race: Any

Subjects- see below

1. Provide target # of subjects (at all sites) needed to complete protocol.

Answer/Response:

100 participants

2. Describe expected rate of screen failure/ dropouts/withdrawals from all sites.

Answer/Response:

Minimal.

Once the patient consents to the study, it is unlikely that they will drop out or withdrawal afterwards given that this is part of a usual care pain management protocol. No extra follow up is required for patients and all the outcomes will be part of a usual post-op data that will be recorded in Epic.

3. How many subjects will be enrolled at all sites?

Answer/Response:

This is a single site study – enrollment at UVA only.

4. How many subjects will sign a consent form under this UVA protocol?

Answer/Response:

All participants (100)

Inclusion/Exclusion Criteria

1. List the criteria for inclusion

Answer/Response:

- All female patients who are 18 years or older who will undergo unilateral or bilateral abdomen-based free flap breast reconstruction at UVA Medical Center from February 2021 to January 2024.

2. List the criteria for exclusion

- Answer/Response: Subjects with ages <18 years

- Allergy to local anesthetic
- Inability to tolerate usual postoperative pain management regimen (Tylenol, Toradol, and Oxycodone PRN) for any reason
- Subjects who cannot read or understand English
- Subjects who are pregnant (self-reported)

3. List any restrictions on use of other drugs or treatments.

Answer/Response: None

Statistical Considerations

1. Is stratification/randomization involved?

Answer/Response: Yes

► IF YES, describe the stratification/ randomization scheme.

Answer/Response:

Random number generator will be used to enroll a subject into control TAP vs. Exparel TAP block group after consent is obtained before surgery. Patients will be blinded to their TAP block method. Surgeons/PI/ study coordinators will not be blinded to randomization. Surgeons/ PI/ study coordinators will have access to the randomization scheme.

► IF YES, who will generate the randomization scheme?

	Sponsor
	UVA Statistician.  Answer/Response:
	UVA Investigational Drug Service (IDS)
	Other:  Answer/Response: Study coordinator/ medical staff in plastic surgery clinic

2. What are the statistical considerations for the protocol?

Answer/Response:

- This is a randomized, prospective trial that examines the effectiveness of Exparel TAP block (mix of Exparel + plain bupivacaine) compared to plain bupivacaine TAP block at University of Virginia Medical Center between February 2021 and January 2024. Patient information will be kept confidential and all identifying information will be removed. Data collected will involve:
 - General Demographic Data: age, gender, race, ethnicity, medical and surgical history, psychiatric history, medications, drug, smoking, alcohol abuse, occupation
 - Type of Reconstructive Procedure: procedure type, laterality

- TAP block information: liposomal bupivacaine vs. plain bupivacaine
- Post-operative Narcotic Requirement: total mg of oral opioid use in postop period during hospitalization and immediate post-operative period (30 days after discharge).
- Post-operative Data: LOS, pain scores, PONV incidence
- Complications

3. Provide a justification for the sample size used in this protocol.

Answer/Response: The primary outcome variable used for sample size calculation is post-operative narcotic requirement. Since we are unsure of the exact standard deviation for the population in terms of narcotic requirement, but we do have a limited number of patients that will be available for the study, we used four different standard deviations to confirm that we would have enough patients for 80% power ($\alpha = 0.05$) to detect a difference in groups. We believe that the estimate of the standard deviation is most likely in the 10 mg range, so having 50 patients in each group would allow us to detect a difference of 5.66 mg between groups at 80% power.

Sample sizes	Standard deviation	Alpha	Power	Difference that can be detected
50 50	1	0.05	80%	0.57 mg
50 50	5	0.05	80%	2.83 mg
50 50	10	0.05	80%	5.66 mg
50 50	15	0.05	80%	8.49 mg

4. What is your plan for primary variable analysis?

Answer/Response:

Univariate analysis with $\alpha < 0.05$ considered significant, variables with $p < 0.1$ will be included in multivariate analysis to control for potential confounding variables and attempt to determine independent factors associated with outcomes.

Primary outcomes will include post-op recovery data- pain scores and postop narcotic requirement (total mg of opioids) both during hospitalization and up to 30 days after discharge. Secondary outcomes will include LOS and incidence of PONV.

5. What is your plan for secondary variable analysis?

Answer/Response:

Secondary outcomes will include LOS and PONV.

Two-sample t-tests or Mann-Whitney U tests will be employed for secondary variable analysis.

Exploratory multivariate analysis will be employed to determine potential confounding variables and attempt to determine the focus for future studies to determine independent factors associated with various outcomes.

6. Have you been working with a statistician in designing this protocol?

Answer/Response: Yes

IF YES, what is their name?

Answer/Response: [name]

7. Will data from multiple sites be combined during analysis?

Answer/Response: No

Study Procedures-Biomedical Research

1. What will be done in this protocol?

Answer/Response:

Participants will either receive plain bupivacaine TAP block (control/ usual care) or Exparel TAP block mix (experimental/ mix of Exparel and plain bupivacaine). Post-op data will be recorded in Epic and will be analyzed.

All the subjects will be recruited in UVA plastic surgery clinic when qualifying patients come in for pre-operative visits.

2. If this protocol involves study treatment, explain how a subject will be transitioned from study treatment when they have completed their participation in the study.

Answer/Response: N/A

Subject Compliance with Study Procedures

1. Explain how the study team will monitor the subject for compliance with the study procedures.

(e.g. study team will administer study drug/ study interventions, study drug inventory of dispensed and returned drug, diary etc.)

Answer/Response: N/A

2. Describe criteria for when a subject is considered to be non-compliant with study procedures.

(e.g. subject returns more than 20% of the study drug, subject misses 20% of study visits)

Answer/Response: N/A

Bibliography

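### The hypothesis is that Exparel controls pain for longer, but no outcome or analysis is timed from the block, so a claim of longer effect would be unsupported

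*Combined protocol and SAP*

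**What the plan says.** Objectives/Hypothesis states: "We hypothesize that liposomal bupivacaine (Exparel) TAP block will provide longer pain control compared to plain bupivacaine TAP block". The Background gives the mechanism and its expected result, namely that Exparel "will provide longer regional blocking effect, hence aiding in pain control and recovery postoperatively".

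The outcomes are these:

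- **Primary, in hospital:** "Primary outcome = post-op pain scores during hospitalization, post-op narcotic pain medication use during hospitalization". The third primary outcome is narcotic use within 30 days of discharge.
- **Secondary:** "Secondary outcome = Length of stay, Post-op nausea and vomiting (PONV").
- **Opioid measure** (Statistical Considerations, question 2): "total mg of oral opioid use in postop period during hospitalization and immediate post-operative period (30 days after discharge").
- **Other post-operative data** (same list): "Post-operative Data: LOS, pain scores, PONV incidence".

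The primary analysis is univariate, followed by a multivariate model (question 4). Secondary outcomes are compared by t-test or Mann-Whitney test (question 5).

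The control block is plain bupivacaine. The experimental block is the "Exparel TAP block mix (experimental/ mix of Exparel and plain bupivacaine"), according to Study Procedures, question 1. Under Human Participants, the data source is described thus: "all the outcomes will be part of a usual post-op data that will be recorded in Epic".

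**The concern.** Longer control is a statement about when the arms differ. To test it, outcomes must be placed on a clock that starts at the block. The plan has no such clock. Its only division of time is at discharge, which falls at a different time for each patient and depends on length of stay, itself a secondary outcome.

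Timing matters particularly here because both arms receive plain bupivacaine. On the plan's own reasoning, the extra benefit of Exparel should appear mainly once the plain drug has worn off. Two things are at stake:

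- **Interpretation.** A favourable result over the whole stay could come from a stronger block in the first hours, a longer block, or both. The planned comparisons would not tell these apart.
- **Sensitivity.** If the benefit is confined to part of the stay, pooling that part with the rest makes it harder to detect.

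**Working it through.** **1. The plan's own figure.** Inputs from Statistical Considerations, question 3: 50 per arm, SD 10 mg, alpha 0.05, power 80%. A two-sided two-sample t-test gives a detectable difference of 5.659 mg, against 5.66 mg stated. The other rows reproduce too: 0.566, 2.829 and 8.488 mg for SDs of 1, 5 and 15 mg, against 0.57, 2.83 and 8.49 mg. The arithmetic is sound. The point concerns what is measured, and the sample-size text does not say which time window the narcotic requirement covers.

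**2. Each outcome against the hypothesis.**

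| Outcome | Window in the plan | Timed from the block? |
|---|---|---|
| Pain scores | Hospital stay; no time points or summary | No |
| In-hospital opioid use | Hospital stay, total mg | No |
| Opioid use after discharge | 30 days from discharge | No |
| Length of stay | Whole stay | Does not measure duration of analgesia |
| PONV | Incidence | No |

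No interval, repeated-measures or time-to-event analysis is planned.

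**3. Why a whole-stay summary cannot identify duration.** Assume, for illustration, control daily mean pain of 5, 4, 3, 2 over four days. The documents give no such figures.

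- Control mean: (5+4+3+2)/4 = 3.5.
- Exparel lower by 1 point on days 2–3: (5+3+2+2)/4 = 3.0.
- Exparel lower by 1 point on days 1–2: (4+3+3+2)/4 = 3.0.

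A later effect and an early effect give the same 0.5-point difference.

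**4. Loss of power if the effect is confined to part of the stay.** Assumptions: 1-point effect on 2 of 4 days, daily SD 2, a common between-day correlation r, 50 per arm, two-sided alpha 0.05, t-test. The SD of a mean of k days is 2 × √[(1 + (k−1)r)/k]. The true difference is 1.0 for the two affected days and 0.5 for the four-day mean.

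| r | SD, 2 days | Power, 2 days | SD, 4 days | Power, 4 days |
|---|---|---|---|---|
| 1 | 2.000 | 70% | 2.000 | 24% |
| 0.5 | 1.732 | 82% | 1.581 | 35% |
| 0.3 | 1.612 | 87% | 1.378 | 43% |

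**5. The same check for opioid totals.** Assume that the arms differ by 5.66 mg in one window with SD 10 mg, and that use outside it has no arm difference and SD s. The SD of the total is √(100 + s² + 2 × r × 10 × s), with r now the correlation between use inside and outside the window. Power within the window is 80%. For the total:

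| s (mg) | r = 0 | r = 0.5 |
|---|---|---|
| 5 | 71% | 56% |
| 10 | 51% | 37% |
| 20 | 24% | 19% |

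The documents give no block duration, length of stay or SD by interval. Steps 4 and 5 therefore show direction and a plausible range, not an estimate for this trial.

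**The case against.** The strongest reply is that duration is only the mechanism. The Background goes on to expect better pain control and recovery, and the listed outcomes measure exactly that. Whole-stay opioid use is a sensible pragmatic measure of net benefit. This stands. A reader might infer that the trial tests nothing in its hypothesis, or can never yield evidence on duration. The documents do not support that. The outcomes address the consequence part of the hypothesis, and the Epic record may hold times from which intervals could be built. What is missing is a plan to use them, and intervals chosen after seeing the data would be post hoc.

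A second reply is that the plan never says pain scores will be averaged over the stay. That is also correct: the summary is unspecified, so the four-day mean above is one possible reading. An unspecified summary does not supply a test of duration either.

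Third, it is tempting to say that the design necessarily dilutes the effect. That holds only if the arms are alike early on. The documents give no doses or volumes for either block, so this cannot be checked. If Exparel helped throughout the stay, a total would not dilute.

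Finally, opioid use is divided at discharge, which gives some separation of early from late. It is coarse and not tied to the block, so it does not measure how long the block lasts.

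**Conclusion.** The point holds. The hypothesis is about longer pain control, and nothing in the outcomes or analyses is timed from the block. Followed exactly, the plan could show net benefit but could not distinguish a longer block from a stronger early one. That conclusion rests on the text alone and is firm.

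The loss of power is conditional. It requires the arms to differ mainly after the plain bupivacaine wears off, and a summary that pools the stay. Under the assumptions in step 4, power falls from about 70–87% to 24–43%. The size for this trial cannot be derived from the documents.

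**What to change.** Define pain scores and opioid use in fixed intervals counted from the block, for example 0–24, 24–48 and 48–72 h, drawn from the Epic record. This assumes that the record is time-stamped, which the protocol does not state and the sponsor should confirm. Name in advance the interval that tests longer control, with the summary measure and the method of comparison. Report the arm difference for every interval alongside the whole-stay outcomes, so that an early effect can be seen for what it is. Limit any claim of longer control to this analysis.

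No extra patients or visits are needed. The costs are protocol wording, more detailed extraction, and an advance commitment to one interval. Later intervals will contain fewer scores once patients are discharged, possibly unequally by arm, so the number of patients contributing to each interval should be reported by arm.

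### Three primary outcomes share one unadjusted 0.05 threshold with no rule for success, and the sample size covers a single opioid variable whose period is unclear

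*Combined protocol and SAP*

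**What the plan says.** Objectives/Hypothesis states one hypothesis, that the liposomal block gives longer pain control, and then lists the outcomes: "Primary outcome = post-op pain scores during hospitalization, post-op narcotic pain medication use during hospitalization, post-op narcotic pain medication use after discharge", the last counted within 30 days of discharge. Inpatient and post-discharge opioid use are therefore separate primary outcomes, alongside inpatient pain scores.

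The Statistical Considerations section then says:

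- **Item 2 (data collected)** puts both opioid periods under one heading for narcotic requirement: "total mg of oral opioid use in postop period during hospitalization and immediate post-operative period (30 days after discharge".
- **Item 3 (sample size)** uses one variable and gives no period: "The primary outcome variable used for sample size calculation is post-operative narcotic requirement". It continues "We believe that the estimate of the standard deviation is most likely in the 10 mg range" and concludes that "having 50 patients in each group would allow us to detect a difference of 5.66 mg between groups at 80% power".
- **Item 4 (primary analysis)** sets one significance threshold of 0.05 for the univariate analysis, followed by a multivariate step for variables with p below 0.1. It keeps the plural: "Primary outcomes will include post-op recovery data- pain scores and postop narcotic requirement (total mg of opioids) both during hospitalization", and extends this to 30 days after discharge.
- **Item 1 (randomization)** records that "Surgeons/PI/ study coordinators will not be blinded to randomization".

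No section gives an order among the primaries, an alpha allocation, a requirement that all succeed, or a statement of which result decides the trial. No power statement covers pain scores.

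**The concern.** A trial with several primary outcomes needs a rule linking the results to the conclusion. Without one, a favourable result on any single outcome could be reported as confirming the hypothesis, and the false-positive rate would exceed the nominal 5%. If instead every primary had to succeed, the false-positive rate would be protected but power would fall well below 80%. Under either rule, the 80% in item 3 is not the power of the trial.

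The second problem concerns which outcome the sample size belongs to. The objectives split opioid use into two periods, while item 2 gathers them under one heading. The 10 mg SD and the 5.66 mg difference could describe inpatient use, post-discharge use or the sum, and these need not have the same SD.

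The staff running the study know each patient's allocation and can see outcomes accumulate by arm. This does not change the error rates below. It does mean that a deciding outcome chosen late could not be shown to have been chosen without knowledge of the results.

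**Working it through.** **Inputs from the documents.** 50 per arm; alpha 0.05; power 80%; SD 10 mg as the best guess (1, 5 and 15 mg also tabulated); detectable difference 5.66 mg (all item 3). Three primary outcomes (Objectives/Hypothesis). The plan does not state sidedness; two-sided tests reproduce its table, whereas one-sided 0.05 would need only 39 per arm for 5.66 mg.

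**Assumed, because the documents give no figure.** Correlations between outcomes, shown from 0 to 0.9; one test per outcome; jointly normal test statistics with equal correlations.

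**Step 1: the plan's own figure.** For a two-sided two-sample t-test at alpha 0.05 with 50 per arm, the standardized difference detectable with 80% power is 0.5659 (noncentral t). Multiplied by SDs of 1, 5, 10 and 15 mg this gives 0.57, 2.83, 5.66 and 8.49 mg, which matches the item 3 table. The arithmetic is right for one outcome tested alone.

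**Step 2: any one of the primaries suffices.** Under independence with no true effects, the chance of at least one false positive is 1 − (1 − 0.05)^k. For k = 3 this is 1 − 0.95³ = 0.1426; for k = 2 it is 1 − 0.95² = 0.0975. With common correlation r, the value is 1 minus the probability that all k statistics lie within ±1.96, found by numerical integration.

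**Step 3: all three must succeed.** If each test has 80% power, joint power under independence is 0.8³ = 0.512. Correlated values use the same normal model.

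| Correlation | Error, any of 3 | Power, all 3 |
|---|---|---|
| 0 | 14.3% | 51% |
| 0.5 | 12.5% | 61% |
| 0.7 | 10.9% | 66% |
| 0.9 | 8.4% | 72% |

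If opioid use is read as one total, there are two primaries, and the any-one error is 9.8% at correlation 0 and 7.0% at 0.9.

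**Step 4: cost of splitting alpha** (noncentral t, SD 10 mg, 50 per arm). The most demanding Holm step is alpha divided by the number of primaries.

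| Alpha for one test | Power at 5.66 mg | Detectable at 80% | Per arm for 80% at 5.66 mg |
|---|---|---|---|
| 0.05 | 80% | 5.66 mg | 50 |
| 0.05/2 = 0.025 | 71% | 6.25 mg | 61 |
| 0.05/3 = 0.0167 | 65% | 6.57 mg | 67 |

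**Step 5: what the unclear period could mean.** Suppose 10 mg is the SD of each opioid period and the outcome is their total. The SD of the total is 10 × √(2 + 2r), and the detectable difference is 0.5659 times that:

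- r = 0: SD 14.1 mg, detectable difference 8.0 mg
- r = 0.5: SD 17.3 mg, detectable difference 9.8 mg
- r = 0.9: SD 19.5 mg, detectable difference 11.0 mg

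If 10 mg is already the SD of the total, 5.66 mg stands. The documents do not say which applies.

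**The case against.** The strongest reply is that the plan never says three arm comparisons are each judged at 0.05, nor that one success is enough. Item 4 reads partly as a screen of candidate factors ahead of a multivariate model, and it does not say whether the univariate or the multivariate result decides. The error rates above therefore describe an assumed analysis. This is fair as far as it goes: the per-outcome threshold is inferred. It is nonetheless the direct reading of a primary-analysis item that gives one threshold and no adjustment, and an unstated rule is itself the defect.

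The number of tests is not settled either. The 30-day period in item 4 could be read as applying to pain scores too, so the count could run from two to four. Pain scores have no stated time point or summary measure. Both points stand, and they add to what must be specified.

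The 14.3% is the independent case. Pain and opioid use in the same patients are unlikely to be independent, so the lower figures are more realistic. At a correlation of 0.9 the error is still 8.4%.

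The period figures are illustrative. They need equal SDs of 10 mg in both periods, which nothing in the documents supports. With SDs of 10 and 5 mg and no correlation, the total's SD would be √(100 + 25) = 11.2 mg and the detectable difference 6.3 mg. The tabulated 15 mg row also covers the lower end of the range. That row, however, addresses uncertainty about the size of the SD, not about which outcome it describes.

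Finally, pain scores are at least as close to the hypothesis as opioid use. Preferring the opioid outcome follows the plan's own choice of sample-size variable and is not a judgement on which matters more clinically.

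**Conclusion.** The concern holds and must be fixed. As written, the plan either exceeds a 5% false-positive rate or falls short of 80% power, depending on a rule it does not state. If any one of three primaries suffices, the error is 8.4% to 14.3% for correlations from 0.9 down to 0. If all three are required, with 80% power for each, joint power is 51% to 72% for correlations from 0 up to 0.9. These ranges rest on assumed equal correlations and one test per outcome.

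The 5.66 mg calculation is correct for a single test. It cannot be tied to one listed primary, because the objectives and item 2 treat the opioid period differently. That conflict is in the text and needs no assumption; only the size of its effect on the detectable difference does.

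**What to change.** 1. State which period (inpatient, post-discharge or total) the sample-size variable and its 10 mg SD describe, and where the SD comes from. Make the objectives and items 2, 3 and 4 agree.
2. Name that opioid outcome as the single primary, tested two-sided at 0.05. The 80% power at 5.66 mg carries over only if the 10 mg SD applies to it.
3. Test the other current primary outcomes afterwards in a fixed order, each only if the one before it succeeds. Define one summary measure for pain scores, and state which analysis decides each test. Write the order down before any outcome is compared by arm.
4. If three primaries are kept, apply Holm and restate the worst case at 50 per arm and SD 10 mg: 65% power at 5.66 mg, or 6.57 mg detectable at 80%. With two primaries the figures are 71% and 6.25 mg.

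The cost is wording in the objectives and the statistical items, with no extra patients. The downside is that some outcomes lose the primary label or, under Holm, the stated detectable difference becomes less favourable. Keeping 80% power at 5.66 mg in the three-primary worst case would need 67 per arm, 134 in total against the planned 100. Item 3 says the number of available patients is limited, so this may not be feasible.

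### Pre-operative opioid use has no fixed place in the analysis of total opioid mg, so a few daily users could cost the unadjusted comparison much of its power

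*Combined protocol and SAP*

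**What the plan says.** Under Inclusion/Exclusion Criteria, the trial takes "All female patients who are 18 years or older who will undergo unilateral or bilateral abdomen-based free flap breast reconstruction at UVA Medical Center" within the study dates. The exclusions are age under 18, local anesthetic allergy, not reading or understanding English, self-reported pregnancy, and "Inability to tolerate usual postoperative pain management regimen (Tylenol, Toradol, and Oxycodone PRN) for any reason". None refers to opioid use before surgery. The item "List any restrictions on use of other drugs or treatments" is answered with none.

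Under Statistical Considerations:
- Item 1 (randomization): "Random number generator will be used to enroll a subject into control TAP vs. Exparel TAP block group after consent is obtained before surgery". No stratification factor is named.
- Item 2 (data collected): the outcome is "total mg of oral opioid use in postop period during hospitalization and immediate post-operative period (30 days after discharge". Nothing is subtracted for opioid taken before surgery. Baseline data include "medications, drug, smoking, alcohol abuse, occupation".
- Item 3 (sample size): "The primary outcome variable used for sample size calculation is post-operative narcotic requirement". The team says it is unsure of the SD and tabulates 1, 5, 10 and 15 mg, then adds: "We believe that the estimate of the standard deviation is most likely in the 10 mg range". With 50 per group this gives a detectable difference of 5.66 mg at 80% power.
- Item 4 (primary analysis): a univariate analysis judged at 0.05. Variables with p below 0.1 then go into a multivariate model. No covariate is fixed in advance, and pre-operative opioid use is not named as a candidate.

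**The concern.** A woman who takes an opioid daily before surgery can meet every criterion. Her habitual oral intake adds to her total whichever block she receives. That part of the total carries no information about the treatment, but it adds to the variance that the comparison has to overcome.

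The target difference is small in absolute terms, 5.66 mg against an SD of 10 mg. A handful of patients with totals tens of mg higher could therefore widen the spread well past the planning value. In a trial of 100 without stratification, an uneven split of those few patients could also shift the observed difference by about as much as the effect sought. The information needed to identify them is already collected, but the plan gives it no assured role.

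**Working it through.** **Inputs from the plan.** 50 per group, alpha 0.05, 80% power, SD 10 mg (item 3). Sidedness is not stated.

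**The plan's own figure.** For a two-sided two-sample t-test with 98 degrees of freedom (noncentral t), the detectable difference is 0.5659 × SD. This gives 0.57, 2.83, 5.66 and 8.49 mg for SD 1, 5, 10 and 15 mg, matching all four rows. A one-sided test gives about 4.97 mg at SD 10 and does not match. The 5.66 mg is correct arithmetic, conditional on the SD.

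**Assumptions, not in the documents.** A share f of patients are daily users, f = 3%, 5% or 10%. Each adds S mg to her total. An intake of 15 to 30 mg/day over a 4-day stay gives S = 60 to 120 mg; S = 10 mg is included as a mild case. The SD around each group's mean stays at 10 mg.

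**Formula.** Overall SD = √(10² + f(1 − f)S²). For f = 5% and S = 120: √(100 + 0.0475 × 14,400) = √784 = 28.0 mg, and the detectable difference is 0.5659 × 28.0 = 15.8 mg.

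| f | S (mg) | Overall SD (mg) | Detectable difference (mg) | Unadjusted power for 5.66 mg |
|---|---|---|---|---|
| 3% | 10 | 10.1 | 5.7 | 79% |
| 5% | 10 | 10.2 | 5.8 | 78% |
| 10% | 10 | 10.4 | 5.9 | 77% |
| 3% | 60 | 14.3 | 8.1 | 50% |
| 5% | 60 | 16.5 | 9.3 | 40% |
| 10% | 60 | 20.6 | 11.7 | 27% |
| 3% | 120 | 22.8 | 12.9 | 23% |
| 5% | 120 | 28.0 | 15.8 | 17% |
| 10% | 120 | 37.4 | 21.1 | 12% |

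**Chance imbalance.** Each extra user in one arm moves the mean difference by S/50. Suppose 5 of the 100 are users. With exactly 50 per arm, a 4:1 or 5:0 split has hypergeometric probability 2 × (0.1529 + 0.0281) = 0.362. If each patient is allocated independently, it is 2 × (5 + 1)/32 = 0.375. A 4:1 split moves the difference by 3 × 60/50 = 3.6 mg or 3 × 120/50 = 7.2 mg.

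**What adjustment recovers.** If all users share the same excess, a yes/no term for opioid use removes f(1 − f)S² and the residual SD returns to 10 mg. Simulated power with that term fixed was about 79% to 81% for 3, 5 or 10 users and S of 30 to 100 mg.

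If the excess varies between users with SD τ, a residual variance of 100 + fτ² remains. For f = 5%, mean excess 60 mg and τ = 30 mg:
- adjusted: √(100 + 0.05 × 900) = √145 = 12.0 mg, detectable difference 0.5659 × 12.0 = 6.8 mg;
- unadjusted: √(145 + 0.0475 × 3,600) = √316 = 17.8 mg, detectable difference 10.1 mg.

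Adjustment then recovers most of the loss, but not all of it.

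**The case against.** The strongest reply is that the plan already has an adjustment step. If opioid use is coded as a candidate variable, the p<0.1 screen will almost surely admit it where it matters. In simulation with 3, 5 or 10 users and 60 or 120 mg excess, it passed in about 100% of trials, and power after inclusion was 79% to 82% when users shared one excess. Where the screen may miss it, at 10 mg excess, little is lost anyway. This stands, and it means that the losses in the table belong to the unadjusted comparison only. It does not close the gap. Item 4 attaches the significance rule to the univariate analysis, does not say whether the adjusted result is primary, and does not list opioid use as a variable to be derived from the medication data.

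A second reply is that a rank test would resist a few extreme totals. The plan names the Mann-Whitney test for the secondary variables only.

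A third is that broad eligibility suits a usual-care comparison with few available patients. That is a fair choice, and the fix leaves it intact.

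A reader might also infer more than the documents support:
- **That the planning SD describes patients without prior opioid use.** No source population is given, and the team says it is unsure of the value.
- **That daily users push the SD beyond every row of the table.** At 3% and 60 mg the SD is 14.3 mg, inside the 15 mg row.
- **That every daily user passes the tolerance criterion.** It covers the whole usual regimen, for any reason, so some may be excluded by it.
- **That prior opioid use is the strongest predictor of the outcome.** Nothing in the documents ranks predictors.

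**Conclusion.** The point holds as a gap in the analysis plan. Eligibility does not address pre-operative opioid use, the sizing outcome counts it in full, and no fixed covariate deals with it. Under the assumed 3 to 10% daily users with 60 to 120 mg excess, unadjusted power for 5.66 mg is 50% to 12% instead of 80%. With 10 mg excess it is 77 to 79%, a negligible loss. Prevalence, dose and stay are all assumptions, so the size of the harm is uncertain even though the gap is plain.

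It is tempting to read this as bias, or as a reason why such patients must be excluded. Neither follows. Randomization keeps the comparison unbiased on average; what is at risk is precision, and chance imbalance in a single trial of 100. The range above covers a hospital stay only. The plan also counts use for 30 days after discharge, but it does not say which period the 10 mg SD describes, so a stay-plus-30-day excess cannot be set directly against 5.66 mg.

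**What to change.** In item 4, define the primary opioid comparison as a model of total opioid mg with treatment and pre-operative opioid use as a fixed covariate, kept whatever its univariate p-value. Code it yes/no from the medication data already collected, or use baseline daily dose if it is recorded; dose would do better if intake differs widely between users. State that this adjusted estimate is the primary one. Add a sensitivity analysis restricted to patients without pre-operative opioid use.

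The cost is a few lines of analysis wording and the coding of one variable, with no new visits or patients. Excluding these patients would narrow the eligible pool and the generalisability of the result. That is a design choice for the sponsor, and this point does not depend on it.
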